**Table 5-1 Days of treatment for each treatment cycle**

Day	1	2	3	4	5	6	7	8	9	10	11	12	13	14	15	16	17	18	19	20	21	22	23	24	25	26	27	28
Debio 1143	X	X	X	X	X	X	X	X	X	X	-	-	-	-	X	X	X	X	X	X	X	X	X	X	-	-	-	-
Nivolumab	X	-	-	-	-	-	-	-	-	-	-	-	-	-	X 	-	-	-	-	-	-	-	-	-	-	-	-	-

From Cycle 3 onwards, patients may switch to nivolumab infusion of 480 mg IV on D1 q4w, if appropriate as per Investigator request and upon Sponsor agreement. After switching to the D1q4w schedule, this schedule must be maintained thereafter.

In Part A, the Debio 1143 starting dose will be 150 mg/d and up to one dose increment of 50 mg will be allowed. No dose escalation beyond 200 mg/d is foreseen in this study under any circumstances. If 200 mg/d is defined as the optimal RP2D, any patients still ongoing with active treatment at a lower Debio 1143 dose at this time may increase their dose to the RP2D, if the investigator considers it appropriate and accepted by the Sponsor.

Patients remaining on treatment after Cycle 2 is completed may have the nivolumab infusion switched from Cycle 3 onwards to one infusion every 4 weeks instead of two infusions, thus receiving nivolumab at 480 mg intravenously on Day 1 q4w. This switch will be allowed on a per-patient basis, based on the

Investigator's judgement and Sponsor agreement. Once the nivolumab dose is switched, this schedule should be maintained until end of treatment (EOT). Switch back to the initial schedule is not permitted.

**Table 5-2 Study treatment starting doses**

Dose level	Debio 1143 orally, daily for 10 days then 4 days off: D1-D10 & D15-D24 q4w (1 cycle= 4 weeks)	Nivolumab# flat dose, IV, D1 & D15 q4w (1 cycle=4 weeks)
1 (starting dose)	150 mg	240 mg
2 (higher dose)	200 mg	

D= day; IV= intravenous; q4w= every 4 weeks

# From Cycle 3, a switch to 480 mg q4w (Day 1 of each 28-day cycle) will be allowed on a per-patient basis, based on the Investigator's judgement and Sponsor's agreement. Once the nivolumab dose is switched, this schedule should be maintained until EOT.

In Part B, patients will receive Debio 1143 at the RP2D established in Part A, in combination with nivolumab at the standard dose. Per-patient dose adjustments of Debio 1143 will be considered according to the severity of any eventual observed toxicity (See [Section 5.4](#))

Participants are planned to be treated with Debio 1143 and nivolumab for up to 52 weeks (i.e., 13 cycles), until any of the following events occurs: symptomatic progressive disease (PD), asymptomatic but confirmed PD (as per iRECIST), unacceptable toxicity (per Investigator judgment and despite up to two dose adjustments), patient withdrawal, or treatment delay greater than 4 and 8 weeks (+1 week tolerance) for Debio 1143 and nivolumab, respectively (see [section 8.3.2.1](#) for details).

Permission to prolong the study treatment for one additional year can be exceptionally granted by the Sponsor, if patients are deriving continuous clinical benefit from the study treatment. Medical justification for extending the treatment and the assessment of the risk/benefit balance must be provided by the Study Investigator and will be discussed with the Sponsor. The decision to further extend study treatment will be re-evaluated on a yearly basis for each patient.

#### 5.4. Dose modifications

For participants without DLT in the previous cycle and/or unacceptable toxicity, in the absence of symptomatic disease progression or confirmed iRECIST PD, the combination therapy can be continued unchanged as long as re-treatment criteria are met (cf. [Table 5-3](#)).

**Table 5-3 Re-treatment criteria**

Assessment	Debio 1143		Nivolumab
	Days 1 and 15	Days 2-10 or 16-24	Days 1 & 15
ECOG-PS	≤1	≤2	≤1
ANC	≥ 1.5 x10  /L	≥ 1.0 x10  /L	-
Platelets	≥ 100 x10  /L	≥ 75 x10  /L	-
Hemoglobin	≥ 9.0 g/dL	≥ 9.0 g/dL	≥ 9.0 g/dL
Total bilirubin	grade 1	grade 2 a	grade 1
AST/ALT	grade 1	grade 2 a	grade 1
Amylase or lipase increases	≤ Grade 3 b		-
Serum creatinine	≤ 2.0 x ULN	-	≤ 2.0 x ULN
Non-optimally treated, symptomatic immune-related AEs	-		≤ Grade 1 c
Any Debio 1143 drug-related AEs	≤ Grade 1 c	≤ Grade 2	-
Cardiac safety/ ECG	Baseline status		
βHCG urine pregnancy test (for women of childbearing age) d	Negative	-	Negative

ANC: absolute neutrophil count; AST/ALT: aspartate aminotransferase/alanine aminotransferase; AEs: adverse event(s); ECG: electrocardiogram; ECOG-PS: Eastern Cooperative Oncology Group performance status

- Provided that total bilirubin and/or ALT/AST levels were Grade 1 as per NCI-CTCAE v5.0 at the start of the corresponding cycle.
- As per NCI-CTCAE v5.0, Grade 3 is defined as amylase or lipase increases up to 5x ULN symptomatic or not; or above 5x ULN but asymptomatic
- Up to Grade 2 for alopecia, stable sensory neuropathy, fatigue/asthenia, skin toxicity or non-optimally treated nausea, vomiting or diarrhea or any grade endocrinopathy optimally treated by replacement therapy
- On every Day 1 for both Debio 1143 and nivolumab

From Cycle 2, if a patient does not meet the requirements for treatment continuation on Day 1 of any cycle, both study drugs will be withheld until recovery or for a maximum of 4 and 8 weeks (+1 week tolerance window) for Debio 1143 and nivolumab, respectively. After this delay-period, treatment should be withdrawn. If a delay occurs in initiating Cycle 2 and is due to any toxicity related to study drug, it will be considered as a DLT.

If a patient does not meet the requirements for treatment continuation on any day other than D1 (D2-10 or D15-24) of any cycle, treatment will be immediately interrupted and the corresponding Debio 1143 dose (and nivolumab if on D15) will be omitted. Patients should be re-assessed, ideally, every 48-72 hours, if clinically indicated, and treatment will only be resumed after all re-treatment criteria are met. On D1, treatment can be delayed more than 3 days if required; in this case, the assessment schedule will shift accordingly, and all assessments planned for D1 will be performed on the day treatment is re-started. However, if treatment is interrupted during any day other than D1 and the re-treatment criteria are not met within 72 hours, treatment will be resumed only on D1 of the next cycle.

A maximum delay of 4 and 8 weeks (+1-week tolerance) for Debio 1143 and nivolumab, respectively, is allowed. After this delay-period, treatment will be withdrawn. Patients withdrawing from treatment for any reason will be followed for safety up to 5 months (±15 days) after the last nivolumab infusion, complete resolution or stabilization of any ongoing toxicity, unless the patient starts a new treatment, end-of-life-care or withdraws consent.

Patients experiencing immune-related AEs, that require withholding nivolumab infusions temporarily until resolution to at least Grade 1, may withhold nivolumab for a maximal period of up to 8 weeks (±1 week

tolerance). During this period, patients may continue to receive Debio 1143 as per protocol, if appropriate. Patients requiring more than 8 weeks ( $\pm 1$  week) of nivolumab interruption and those who permanently discontinue nivolumab for any reason, will discontinue Debio 1143 permanently and will be withdrawn from the study. The nivolumab dose will not be adjusted under any circumstances.

Patients experiencing any treatment-related grade 4 toxicity (clinically or laboratory, excluding grade 4 amylases and/or lipase and/or non-febrile neutropenia) will withdraw from treatment definitively without further reduction (see [section 8.3.2.1](#) for details).

Patients experiencing any other treatment-related toxicity fulfilling applicable DLT criteria (as shown below) at any time during the study must stop treatment and may only resume treatment after adequate recovery to re-treatment criteria.

Treatment must be re-started with a Debio 1143 dose reduction. Individual patients may have up to two dose adjustments of 50 mg/d (each one) up to a minimum dose of 100 mg/d Debio 1143 (i.e. 1st dose reduction 150 mg/d, 2nd dose reduction 100 mg/day). Patients still requiring a dose adjustment with a dose of 100 mg/d will be withdrawn from the study. Once adjusted, Debio 1143 dose will not be re-escalated under any circumstances.

Up to 2 dose reductions must be implemented in the event of any of the following:

- Any Debio 1143-related Grade 4 hematologic toxicity
- Debio 1143-related febrile neutropenia any grade, or Grade 3 thrombocytopenia if associated with bleeding or requiring platelet transfusion
- Debio 1143-related grade 2 or higher alanine transaminase (ALT)/ aspartate transaminase (AST) increase with a concurrent increase of total bilirubin  $\geq 2$  x upper limit of normal (ULN) and concurrent with alkaline phosphatase (ALP)  $\leq 2$  x ULN (Hy's law), in the absence of objective causes of biliary obstruction due to obvious disease-related causes
- Any Grade 3, treatment-related, non-hematologic clinical toxicity lasting 3 or more days despite optimal supportive care, or requiring admission for appropriate medical management; hypersensitivity and/or infusion-related reactions are excluded if not reoccurring after appropriate pre-medication and/or prolonging infusion time
- Grade 3 non-hematologic laboratory value (excluding lipase, amylase and/or autoimmune endocrinopathies manageable by replacement therapies)
- A delay of  $>2$  weeks due to drug-related toxicity in initiating subsequent cycles, or a second delay lasting  $>24$  h but  $<2$  weeks
- Unable to complete at least 70% of the scheduled treatment, i.e. more than six Debio 1143 skipped doses during any cycle due to treatment-related toxicity or more than 2 treatment interruptions  $>24$  h but  $<6$  days

If for any reason Debio 1143 is withheld temporarily, nivolumab will also be withheld until treatment may be resumed. Patients discontinuing Debio 1143 definitively for any reason will also discontinue nivolumab study treatment.

Patients requiring no more than 1 treatment interruption per cycle and for not more than 3 consecutive days, may resume treatment without dose adjustments. Patients requiring one interruption greater than 3 days, or more than one interruption during any given cycle, may resume treatment only after full recovery and adjustment of Debio 1143 dose upon the Sponsor's agreement (if applicable).

Patients interrupting treatment or delaying the start of a new cycle due to any Grade 3 treatment-related toxicity will resume treatment after Debio 1143 adjustment (except Grade 3 neutropenia, thrombocytopenia, non-optimally treated fatigue, diarrhea, or nausea). Patients experiencing any Grade 4 treatment-related toxicity will immediately stop treatment without any possible therapy resumption.

Omitted Debio 1143 doses will not be re-administered under any circumstances. Every new cycle D1 will start with the Debio 1143 dose. In case of any cycle delays (Day 1 delayed greater than 72 hours), all

subsequent doses will be administered according to the new planning, if feasible (i.e. Day 1-10 followed by Day 11-14 pause).

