
Table 2: Re-treatment criteria			
Assessment	Debio 1143		Nivolumab
	Days 1 & 15	Days 2-10 or 16-24	Days 1 & 15
ECOG-PS	≤1	≤2	≤1
ANC	≥ 1.5 x10  /L	≥ 1.0 x10  /L	-
Platelets	≥ 100x10  /L	≥ 75 x10  /L	-
Hemoglobin	≥ 9.0 g/dL	≥ 9.0 g/dL	≥ 9.0 g/dL
Total bilirubin	Grade 1	Grade 2 a	Grade 1
AST/ALT	Grade 1	Grade 2 a	Grade 1
Amylase or lipase increases	≤ Grade 3 b		-
Serum creatinine	≤2.0 x ULN	-	≤ 2.0 x ULN
Non-optimally treated, symptomatic immune-related AEs	-		≤ Grade 1 c
Any Debio 1143 drug-related AEs	≤ Grade 1 c	≤ Grade 2	-
Cardiac safety /ECG	Baseline status		
βHCG urine pregnancy test (for women of childbearing age) d	Negative	-	Negative

ANC: absolute neutrophil count; AST/ALT: aspartate aminotransferase/alanine aminotransferase; AEs: adverse event(s); ECG: electrocardiogram; ECOG-PS: Eastern Cooperative Oncology Group performance status
 
a) Provided that total bilirubin and/or ALT/AST levels were Grade 1 as per NCI-CTCAE v5.0 at the start of the corresponding cycle.
 
b) As per NCI-CTCAE v5.0, Grade 3 is defined as amylase or lipase increases up to 5x ULN symptomatic or not; or above 5x ULN but asymptomatic
 
c) Up to Grade 2 for alopecia, stable sensory neuropathy, fatigue/asthenia, skin toxicity or non-optimally treated nausea, vomiting or diarrhea, or any grade endocrinopathy optimally treated by replacement therapy
 
d) On every Day 1 for both Debio 1143 and nivolumab
			
PARTICIPANT DURATION	
A 4-week period is planned for patient screening before initiating the study treatment.
 
The treatment duration for an individual patient is 52 weeks (13 cycles). If a patient is benefiting from the study treatment, exceptional permission to prolong the study treatment might be granted. After the end-of treatment (EOT), patients will be followed every 12 weeks (± 1 week window) until symptomatic or confirmed PD or start of new cancer treatment or end-of-life care, or until the end of the Main study period (lasts until 18 months after LPI or 60 days after last patient last visit [LPLV]), whichever occurs first. For patients who continue study treatment after the Main study period, tumor response assessments will continue at the frequency of local institutional care practice until EOT.
		

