**Study treatments**

Patients will receive oral Debio 1143 at a starting dose of 150 mg once daily on Days 1-10 and Days 15-24 every 4 weeks (q4w) along with nivolumab at a flat dose of 240 mg IV on days 1 and 15 of a 28-day cycle (with a possible switch to one dose at 480 mg q4w from Cycle 3) (cf. Table 5-1). On Days 1 and 15, Debio 1143 will be administered on site, immediately before the nivolumab infusion. Remaining daily doses are to be taken by the patient at home following relevant medical instructions, except on days where PK samples are planned, during the first cycle, and the third cycle. For nivolumab administration, specific precautionary measures outlined in section 7.6.2 must be applied.

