#### **7.6.2.2. Peri- and post-infusion procedures**

For the infusion, patients must be observed according to standard applicable institutional guidelines, if applicable, or for approximately 90 minutes post-infusion, in an area with resuscitation equipment and emergency agents. At all times during nivolumab treatment, immediate emergency treatment of an infusion-related reaction or a severe hypersensitivity reaction according to institutional standards must be assured.

Infusion of nivolumab will be stopped in case of Grade  $\geq 2$  hypersensitivity, inflammatory response, or infusion-related reactions. Infusions may be resumed after Grade  $\leq 2$  events upon resolution of the events within less than 4 hours and after medical assessment and agreement by a qualified Investigator. Infusion duration will not be shorter than 120 minutes after resumption in all subsequent infusions.

Treatment will be withdrawn definitively after the occurrence of any Grade  $\geq 3$  infusion-related reactions, hypersensitivity or cytokine-release syndrome. Appropriate standard measures must be in place for the medical management of the patients under these circumstances.

Recommendations on how to manage infusion-related reactions and severe hypersensitivity reactions according to the NCI are outlined in section 7.6.2.3.

When a reaction does not resolve completely after 4 hours despite appropriate medical management, the ongoing infusion will not be resumed. Upon Investigator judgement and agreement, next scheduled infusions should be performed at a slower infusion rate (i.e., 120-180 minutes) and pre-medications with standard anti-H1, non-steroidal anti-inflammatory drugs (NSAIDs) and/or low dose steroids might be considered as per standard institutional guidelines.

See section 7.6.2.4 for details on the management of immune-related AEs and sections 5.4 and 7.6.2.3 for other (not immune-related) adverse drug reactions (ADRs) potentially requiring nivolumab discontinuation or temporarily withhold.

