**Table 7-2 Management of immune-related AEs**

NCI-CTCAE grade v5.0	Suggested management	Suggested follow-up
Gastrointestinal immune-related AEs: diarrhea and/or colitis		
Grade 1 Diarrhea: <4 stools/day over baseline Colitis: asymptomatic	
 
• May continue nivolumab therapy
 
• Evaluate symptomatic treatment (e.g. loperamide)
 
	
 
• Close monitoring for symptoms worsening
 
• Educate patient to report if worsening immediately
 
• If worsens: treat as Grade 2 or 3/4
 
• GI consultation may be needed for persistent cases (e.g. more than 4 weeks)
 

Grade 2 Diarrhea: 4 to 6 stools per day over baseline; IV fluids indicated <24 h; not interfering with activities of daily living Colitis: abdominal pain; blood in stool	
 
• Withhold temporarily nivolumab therapy until resolution to Grade 1
 
• Symptomatic treatment if infection is ruled out
 
• Consider GI consultation
 
• Consider 1 mg/kg/day prednisone or equivalent
 
	
 
• If improves to Grade ≤1: resume nivolumab therapy
 
• If persists ≥3 to 5 days or recurs: treat as Grade 3 or 4
 

Grade 3 to 4 Diarrhea (grade 3): ≥7 stools per day over baseline; incontinence; IV fluids ≥24 h; interfering with activities of daily living Colitis (grade 3): severe abdominal pain, medical intervention indicated, peritoneal signs Grade 4: life-threatening, perforation	
 
• Withhold temporarily nivolumab therapy for Grade 3, if first occurrence.
 
• Permanently discontinue study treatment for Grade 4 or recurrent Grade 3.
 
• 1 to 2 mg/kg/day prednisone IV or equivalent
 
• Add prophylactic antibiotics for opportunistic infections
 
• Consider lower endoscopy
 
• Consider early infliximab treatment (5-10 mg/kg) if symptoms are steroids-refractory after 2-3 days.
 
	
 
• If improves: continue steroids until Grade 1, then taper over at least 4-6 weeks; resume nivolumab therapy following steroids taper (for initial Grade 3).
 
• If worsens, persists ≥2 to 3 days, or recurs after initial improvement: add infliximab (5-10 mg/kg, if no contraindication)
 

NCI-CTCAE grade v5.0	Suggested management	Suggested follow-up

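### Footnote c of Table 5-3 lets Grade 2 immune-related diarrhoea pass the nivolumab re-treatment check, although Table 7-2 withholds nivolumab until Grade 1: a minor safety-wording correction

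*Protocol*

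**What the plan says.** **The re-treatment check.** In Protocol section 5.4, Table 5-3 has a nivolumab row for Days 1 and 15 labelled "Non-optimally treated, symptomatic immune-related AEs". Its limit is Grade 1 or less, with footnote c on the nivolumab cell. Footnote c reads "Up to Grade 2 for alopecia, stable sensory neuropathy, fatigue/asthenia, skin toxicity or non-optimally treated nausea, vomiting or diarrhea" and goes on to endocrinopathy controlled by replacement therapy. Synopsis Table 2 has the same row and footnote. Section 5.4 opens by allowing the combination to continue unchanged while these criteria are met, for patients without a DLT in the previous cycle and/or unacceptable toxicity.

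**The immune-related management table.** For Grade 2 diarrhoea or colitis, Table 7-2 in section 7.6.2.4 says: "Withhold temporarily nivolumab therapy until resolution to Grade 1". Its follow-up column adds: "If persists ≥3 to 5 days or recurs: treat as Grade 3 or 4".

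**Text bearing on which table applies.**
- Section 5.3: "For nivolumab administration, specific precautionary measures outlined in section 7.6.2 must be applied".
- Section 5.4 refers to immune-related events "that require withholding nivolumab infusions temporarily until resolution to at least Grade 1" and caps such holds at 8 weeks (±1 week).
- Section 7.6.2.2 sends the reader to section 7.6.2.4 for immune-related events, and to "sections 5.4 and 7.6.2.3 for other (not immune-related) adverse drug reactions (ADRs) potentially requiring nivolumab discontinuation or temporarily withhold".
- Section 7.6.2.4 says that treatment of immune-related events should follow the guideline summarised in Table 7-2.

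**The concern.** Table 5-3 is the list a site checks before each infusion. On a dosing day, a patient with Grade 2 immune-related diarrhoea passes its nivolumab column because of footnote c, while Table 7-2 holds the infusion. A site that opens only Table 5-3 is not stopped from giving nivolumab during an event the protocol elsewhere wants held.

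The footnote cannot be set aside as a Debio 1143 note that strayed into the wrong cell. Two of its other items suit an immune-related row and agree with Table 7-2: skin toxicity up to Grade 2, where Table 7-2 continues nivolumab, and endocrinopathy on replacement, where Table 7-2 allows resumption once the patient is stable. A reader has good reason to apply the footnote to immune-related events, and diarrhoea is the item that clashes. What is at stake is patient safety at a single dosing decision, not the trial's inference.

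**Working it through.** No figure in the plan is in question, so the check sets the rules side by side for one patient on a nivolumab dosing day with suspected immune-related diarrhoea or colitis.

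| Situation | Table 5-3, nivolumab column | Table 7-2 | Do they differ? |
|---|---|---|---|
| Grade 1 diarrhoea | Passes | May continue | No |
| Grade 2 diarrhoea, not escalated, no steroid above 10 mg/d | Limit raised to Grade 2 by footnote c: passes | Withhold until Grade 1 | **Yes** |
| Grade 2 colitis | Not named in footnote c: limit Grade 1, fails | Withhold until Grade 1 | No |
| Grade 3 diarrhoea | Fails | Withhold at first occurrence; stop if recurrent | No |

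The row covers only non-optimally treated, symptomatic events. Optimally treated Grade 2 diarrhoea is outside the row, so it is not stopped by it either.

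**Does another rule hold nivolumab in the second row?** Section 5.4 withholds nivolumab whenever Debio 1143 is withheld. The Debio 1143 row for drug-related events carries the same footnote c on Days 1 and 15, and allows Grade 2 on the other dosing days. This diarrhoea therefore does not trigger the linked hold.

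**What if the event is escalated?** If it persists for 3 to 5 days or more, or recurs, Table 7-2 treats it as Grade 3 or 4, with prednisone at 1 to 2 mg/kg/day. That exceeds 10 mg/d in any adult.
1. Section 7.7.2 lists systemic corticosteroids above 10 mg/d as prohibited. It allows them for treatment-related events after Debio 1143 is interrupted.
2. Section 5.4 then withholds nivolumab because Debio 1143 is withheld.
3. Section 7.7.1 adds that patients needing prolonged steroids above 10 mg/d should stop study treatment, subject to risk and benefit.

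Nivolumab is therefore held on this branch whatever Table 5-3 says. The same chain applies to a Grade 2 patient started on the 1 mg/kg/day that Table 7-2 asks the site to consider.

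**Size.** The difference is confined to un-escalated Grade 2 immune-related diarrhoea on a dosing day. It concerns one infusion: 240 mg on Day 1 or Day 15, or 480 mg on Day 1 for a patient switched from Cycle 3. The documents give no rate for this event on a dosing day, so the number of patients cannot be stated.

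**Is precedence stated?** Sections 5.3, 5.4, 7.6.2.2 and 7.6.2.4 lean towards Table 7-2. None says that it overrides the immune-related row or footnote c of Table 5-3.

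**The case against.** The strongest reply is that the direction is already settled. Section 7.6.2.2 deals with withholding nivolumab: it assigns immune-related events to section 7.6.2.4 and cites section 5.4 for reactions that are not immune-related. Section 5.3 makes the section 7.6.2 precautions mandatory. Section 5.4 itself describes immune-related holds to Grade 1. Table 5-3 is only a minimum condition: it permits an infusion and never orders one. A careful investigator would hold.

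Most of this stands. A reader might infer that the two tables compel opposite actions, or that the protocol leaves the choice wide open. The documents support neither reading, since holding meets both tables and the cross-references favour Table 7-2.

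The reply does not remove the printed allowance:
- The pointer in section 7.6.2.2 does not fit a section 5.4 table that has its own immune-related row for nivolumab.
- The section 5.4 text covers events that need a hold without saying which ones do.
- Table 7-2's action column is headed as suggested management.
- The general Grade 1 to 2 guidance that opens section 7.6.2.4 mentions symptomatic treatment, moderate-dose steroids and closer monitoring, but no hold.

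A reader might also infer that several infusions are at stake, because Table 7-2 requires a steroid taper of at least 4 to 6 weeks after escalation. That is not supported either. It takes the alternative to be uninterrupted dosing, whereas sections 7.7.2 and 5.4 already lead to a hold once such steroids start.

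**Conclusion.** The point holds as a minor safety-wording correction. Footnote c raises the nivolumab limit to Grade 2 for non-optimally treated diarrhoea in a row about immune-related events. Table 7-2 withholds nivolumab for that event until Grade 1, and no sentence overrides the footnote.

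The consequence is whether, or when, a single nivolumab infusion of 240 mg or 480 mg is given. It arises only if the diarrhoea is judged immune-related, is Grade 2 on a dosing day and has not been escalated to steroids above 10 mg/d, and if the site relies on Table 5-3 alone. How often this happens is unknown. The primary endpoints, the futility and efficacy boundaries and the sample size are unaffected.

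**What to change.** In Table 5-3 and synopsis Table 2, exclude immune-related diarrhoea from footnote c in the nivolumab column, and keep the allowance for the Debio 1143 row. Add to section 5.4: *For any suspected immune-related AE, Table 7-2 governs nivolumab dosing even when Table 5-3 is met.* The added sentence also covers optimally treated diarrhoea, which the table row does not reach.

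The cost is a wording change in two tables and one new sentence, with no new data. The downside is a few more nivolumab holds, all of which Table 7-2 already asks for.
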